##### **8.1.1 Archival Tissue Correlative Studies**

Archival tissue, preferred to have been collected within 18 months of enrollment otherwise, will be obtained prior to study treatment if available. This tissue will be used to assess response to TAK-228, and evaluate mechanisms of acquired resistance to therapy. Mutation profiling will be performed using massively parallel sequencing technology (Oncopanel) and/or whole exome sequencing. In addition, nucleic acid purification will be performed on the specimens.

The archival specimen must contain adequate viable tumor tissue and be overall representative of the whole tumor (i.e. containing predominant and highest Fuhrman grade areas). Formalin-fixed paraffin-embedded tumor tissue blocks are preferred and should contain tumor areas that measure at least 1 cm square in aggregate. Alternatively, a minimum of 20 unstained 4-micron-thick sections (on charged slides) can be provided. The unstained slides should be coated with paraffin. Surgical specimens are preferred with order of preference being 1) nephrectomy specimens and 2) metastatectomy specimens. If surgical specimens are not available, core-needle biopsy specimens are acceptable. Fine-needle aspiration, brushings, cell pellet from pleural effusion, bone marrow aspirate/biopsy are not acceptable.

## **8.1.2 Fresh Tissue Correlative Studies**

### **8.1.2.1 Pre-Treatment**

If subjects do not have archival tissue from within the previous 18 months available, they will undergo one mandatory biopsy prior to study treatment. The pretreatment biopsy must occur within 28-days prior to initiation of study therapy.

### **8.1.2.2 Progression**

In subjects who experience an objective response as defined by RECIST version 1.1 and then subsequent progression as defined by RECIST 1.1, a biopsy will be mandated at the time of disease progression from a site of metastasis, if feasible and safe. Subjects should continue study treatment until the day prior to the progression biopsy. Progression biopsy must occur within 28-days of determination of disease progression.

The metastatic sites need to be safely accessible as deemed by the site investigator and interventional radiologist. During the core needle biopsy procedure, four core samples will be collected: one will be placed in formalin for routine histology and immunohistochemistry (IHC) studies and the remaining three will be frozen in liquid nitrogen. Two of the cores will be utilized for genomic analysis and the remaining core will be used for IHC and immunoblot analysis. In addition, nucleic acid purification will be performed on the specimens.

Biopsies will be obtained in a manner that minimizes risk and will be taken only if there is no intervening condition (e.g., thrombocytopenia or neutropenia) that, in the opinion of the site investigator, increases the likelihood of procedural complications to an unacceptable level.

Biopsies should be performed per institutional standards and/or operator preference. Blood samples will be drawn within 2 weeks of the biopsy to document an acceptable coagulation profile (INR  $\leq$  1.5, PTT  $\leq$  60, platelets  $>$  50,000). Aspirin, clopidogrel, and NSAIDS should be discontinued 5 days prior to the biopsy.

Preferred biopsy sites include: lymph nodes, peripheral based liver lesions, exophytic soft tissue components associated with bone lesions, subcutaneous nodules, pleural-based lesions, and kidney lesions. An 18 gauge needle or larger is preferred when possible. For each tissue

collection procedure, the intent is to acquire at a minimum of 4 cores and up to 6 cores. Though the size of the biopsy cores is variable, to optimize tumor capture, larger cores are preferred.

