#### 5.3 Subject Evaluations

Subjects will be evaluated clinically every week for Cycle 1, every 2 weeks for Cycles 2-3, and then every 4 weeks for subsequent cycles. On the days that a subject is seen in clinic, subjects are not required to physically dose in clinic. There is no in-clinic dosing requirement.

Subjects will undergo disease assessments with imaging every 8 weeks relative to the C1D1 visit and continue on study therapy until radiographic progression, unacceptable toxicity or withdrawal.

Subjects that do not have archived tissue from the previous 18 months available will undergo one mandatory biopsy at screening. The pretreatment biopsy must occur within 28-days prior to initiation of therapy. In subjects who have an objective disease response as per RECIST version 1.1 and then subsequently progress, a second biopsy at time of progression will be mandatory if feasible and safe. Subjects should continue study treatment until the day prior to the progression biopsy. Progression biopsy must occur within 28-days of determination of disease progression.

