### **5.5 Criteria for Taking a Participant Off Protocol Therapy**

Duration of therapy will depend on individual response, evidence of disease progression and tolerance. In the absence of treatment delays due to adverse event(s), treatment may continue until one of the following criteria applies:

- Disease progression
- Intercurrent illness that prevents further administration of treatment
- Unacceptable adverse event(s)
- Participant demonstrates an inability or unwillingness to comply with the oral medication regimen and/or documentation requirements
- Participant decides to withdraw from the protocol therapy
- Investigator determines a change of therapy would be in the best interest of the subject
- Female subject becomes pregnant
- General or specific changes in the participant's condition render the participant unacceptable for further treatment in the judgment of the treating investigator
- Study Termination

Participants will be removed from the protocol therapy when any of these criteria apply. The reason for removal from protocol therapy, and the date the participant was removed, must be documented in the case report form (CRF). Alternative care options will be discussed with the participant.

An ODC Treatment Ended/Off Study Form will be filled out when a participant is removed from protocol therapy. This form can be found on the DF/HCC website at <http://www.dfhcc.harvard.edu/research/clinical-research-support/document-library-forms-sops-etc/>.

In the event of unusual or life-threatening complications, treating investigators must immediately notify the Overall PI, [REDACTED]

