### 6.1 TAK-228 Dose Modifications

TAK-228 administration should be withheld for treatment-related adverse events that are Grade 3 or higher, despite supportive treatment per standard clinical practice. If the event resolves to Grade 1 or Grade 2 for hyperglycemia or rash or to baseline values within 2 weeks of interrupting treatment, then the subject may resume study treatment at a dose reduced by 1 level (see Table below). If study drug administration is delayed for more than 4 weeks (28 consecutive days) due to non-resolving study drug-related grade 3 toxicity despite supportive treatment per standard clinical practice, or more than 3 dose reductions of study drug are required in a subject, then study drug treatment should be stopped, the subject discontinued from the study, and the EOT visit completed within 30 days ( $\pm 7$ ) after the last dose of study drug.

If study drug administration is delayed for more than 6 weeks (42 consecutive days) due to non-treatment related adverse events, then study drug treatment should be discontinued, and EOT visit completed within 30 days ( $\pm 7$  days) after the last dose of study drug

If study drug is delayed for either less than 4 weeks (28 consecutive days) due to non-resolving study drug-related grade 3 toxicity or less than 6 weeks (42 consecutive days) due to non-treatment related adverse events, subjects should skip the dosing cycles missed and when if treatment is resume, this should be at the next scheduled dosing cycle.

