11: Baseline fresh tumor biopsies are MANDATORY for subjects that do not have archival tissue available from the previous 18 months. Screening tumor biopsies must be collected within 28 days prior to initiation of study therapy. Progression tumor biopsies are MANDATORY ONLY in subjects who experience an initial disease response per RECIST 1.1 criteria and then subsequent progression, if feasible and safe.

12: MANDATORY: Blood for germline DNA analysis will be collected prior to C1D1 treatment. MANDATORY: Research blood samples for biomarker analysis to be collected prior to C1D1 treatment and every 8 weeks until off treatment. If off treatment collection is within 2 weeks of prior collection, research samples do not need to be collected.

13: Subjects who discontinue study treatment will return for a treatment discontinuation visit around 30 days ( $\pm 7$  days) after the last study treatment. The visit at which a response assessment shows progressive disease may be used as the treatment discontinuation visit.

14: After a subject discontinues from study treatment, they will continue to be followed for survival and subsequent anti-cancer therapy every 6 months until death or 2 years after study treatment discontinuation. Follow up may be accomplished via clinic visit, phone call, or other avenues as appropriate.

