#### **7.3 Safety Follow-up Visit Evaluations**

Subjects discontinued from the treatment phase of the study for any reason will be evaluated 30 days ( $\pm 7$ ) after the last dose of study drug. Discuss the sequence of events that should occur during the visit, e.g., review of medications, assessment of adverse events, etc. These should be consistent with the Study Calendar.

- Physical Examination including review of medications (over-the-counter or prescribed) and side effects the subject is experiencing
- Vital signs (including temperature, heart rate, blood pressure, weight, height and oxygen saturation) and ECOG performance status
- ECG
- Laboratory Testing
  - CBC with differential and platelet count
  - Comprehensive Metabolic Profile
  - Thyroid Function Tests (TSH)

- Fasting Lipid Profile (fasting is defined as nothing except water and/or medications after midnight or for a minimum of 8 hours before the assessment).
- Urinalysis (Subjects with  $\geq 2+$  protein on dipstick urinalysis at baseline must undergo 24-hour urine collection for protein)
- Progression tumor biopsies are MANDATORY ONLY in subjects who experience an initial disease response per RECIST 1.1 criteria and then subsequent progression, if feasible and safe.

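### Footnote 13 of the study calendar should not let the progression visit replace the post-last-dose visit in responders who keep dosing until biopsy

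*Combined protocol and SAP*

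**What the plan says.** Four provisions meet here.

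- **Dosing past progression.** Sections 5.3 and 8.1.2.2 require a biopsy, if feasible and safe, in subjects who respond by RECIST 1.1 and then progress. Both give the same instruction: "Subjects should continue study treatment until the day prior to the progression biopsy". The timing is "Progression biopsy must occur within 28-days of determination of disease progression".
- **Default visit after the last dose.** Section 7.3: "Subjects discontinued from the treatment phase of the study for any reason will be evaluated 30 days" (±7) after the last dose of study drug. The list includes physical examination, vital signs, ECG, blood count, metabolic profile, TSH, lipids and urinalysis. The first sentence of footnote 13 to the study calendar gives the same timing.
- **Optional substitute.** The second sentence of footnote 13: "The visit at which a response assessment shows progressive disease may be used as the treatment discontinuation visit". No group is excluded.
- **Clinic frequency.** Section 5.3 sets clinical evaluations weekly in Cycle 1, every two weeks in Cycles 2 and 3, "and then every 4 weeks for subsequent cycles".

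**The concern.** The substitute in footnote 13 suits a subject who stops TAK-228 when progression is found: the visit then comes at the end of exposure. It does not suit a responder who has been told to go on dosing until the biopsy. For that subject the progression visit comes before the final doses, yet nothing in the footnote stops a site from recording it as the discontinuation visit.

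If a site does so, the subject has no scheduled examination, ECG, blood count or chemistry after the final doses. The ECG is not a formality for this drug: Section 11.1.1.1 reports one death from ventricular fibrillation and cardiac arrest that was considered related to TAK-228, and the calendar schedules an ECG on Day 1 of each cycle and at discontinuation. What is at stake is patient safety and complete end-of-treatment safety data in a few subjects, not the efficacy analysis.

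**Working it through.** The plan gives no figure on this point, so there is none to reproduce.

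**Inputs.** 30 mg once weekly (5.2); biopsy within 28 days of determination (8.1.2.2); visit 30 ± 7 days after the last dose (7.3); scans every 8 weeks and clinic visits every 4 weeks from Cycle 4 (5.3); 40 subjects, response rates of 5% and 20% (12.3).

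**Step 1: doses after the progression visit.** Call the visit day 0. Assume that progression is determined at that visit and that full weekly dosing is uninterrupted. With biopsy on day B, the last possible dosing day is B − 1. Doses fall on d, d + 7, d + 14 and so on, with d from 0 to 6. Count those after day 0 and no later than day B − 1.

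| Biopsy day B | Visit is a dosing day (d = 0) | Visit is not a dosing day (d = 1 to 6) |
|---|---|---|
| 7 | 0 | 1 |
| 14 | 1 | 2 |
| 21 | 2 | 3 |
| 28 | 3 | 4 |

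For B = 28, d = 0 gives doses on days 7, 14 and 21, and d = 6 gives days 6, 13, 20 and 27. The maximum is 4 × 30 = 120 mg. With d = 0 it is 3 × 30 = 90 mg, not counting the dose due on day 0 itself.

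**Step 2: when the 7.3 visit would fall.** For B = 28 the last dose is on day 21 to 27. The visit is then due between day 21 + 23 = 44 and day 27 + 37 = 64. Under the option it can be recorded on day 0.

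**Step 3: whether another scheduled visit covers the interval.** On scheduled scans, the earliest confirmed responder has a partial response at week 8, confirmation at week 16 and progression at week 24. Since 24/4 = 6 completed cycles, this is Cycle 7 Day 1, when visits are four-weekly. The next Day 1 is day 28 ± 3, that is day 25 to 31. Dosing has stopped by day 27, so this visit falls at about the time the subject leaves treatment and cannot be relied on.

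**Step 4: whether the biopsy itself supplies the visit.** The calendar and 7.3 list the progression biopsy with the discontinuation visit. Under 8.1.2.2 with weekly dosing, a day-28 biopsy falls 28 − 27 = 1 to 28 − 21 = 7 days after the last dose. The 7.3 visit is 23 to 37 days after it. The two occasions do not coincide.

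**Step 5: how many subjects.** Expected responders if all 40 enrol: 40 × 0.05 = 2 (binomial 5th to 95th percentile 0 to 4) or 40 × 0.20 = 8 (4 to 12). At 5%, allowing for the 38% chance of stopping after stage 1 given in 12.3, the mean is 20 × 0.05 + 0.62 × 20 × 0.05 = 1.62. These are responders. The affected are only those who also progress, are biopsied and attend a site using the option. The documents do not give those fractions.

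**The case against.** The strongest reply is that footnote 13 already reads correctly. Its first sentence concerns subjects who discontinue treatment, and a responder told to keep dosing has not yet discontinued at the progression visit. Section 7.3 applies to discontinuation for any reason and does not repeat the substitute. The word in the footnote is permissive. This stands to the extent that a careful site would hold the visit after the last dose, so the text is not wrong as written. It does not remove the gap, because the footnote does not say that these subjects are outside the option.

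A second reply is that little is lost. Safety follow-up runs 90 days from the last dose or until another anticancer therapy (5.6), serious events are reportable to 30 days after the last dose (11.3.1, 11.4.2), home glucose checks continue during dosing, and coagulation and platelets are checked within two weeks of biopsy (8.1.2.2). Three to four doses between clinic visits is also the normal pattern from Cycle 4. All of this stands and keeps the point minor. None of it is a scheduled ECG or chemistry panel after the last dose.

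Three stronger readings may tempt a reader, and the documents do not support them.

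- *That Section 5.5 forbids the pre-biopsy dosing.* It lists disease progression and says "Participants will be removed from the protocol therapy when any of these criteria apply", and 5.3 has subjects "continue on study therapy until radiographic progression, unacceptable toxicity or withdrawal". But the biopsy rule is in 5.3 as well, in the next paragraph, and is repeated in 8.1.2.2. It reads as a specific exception to a general rule.
- *That exposure after the visit could be much larger because progression is read centrally.* The documents give no turnaround time for central review. A subject still on treatment beyond about day 28 would also reach the next Day 1 visit, with examination, ECG, blood count and chemistry.
- *That the sections disagree on which responders are biopsied.* The wording varies a little, but every place ties the response to RECIST 1.1, and 5.3 uses both terms together. Whether confirmation is needed is a separate question of clarification.

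**Conclusion.** The point holds as a cheap improvement to patient safety, of minor weight. If a site uses the substitute in footnote 13 for a responder who keeps dosing, the checks that 7.3 places after the last dose can be missed following up to 3 to 4 further weekly doses, at most 120 mg. That size assumes a day-28 biopsy, determination of progression at the visit and uninterrupted dosing at 30 mg; an earlier biopsy or a reduced dose makes it smaller. The number affected should be no more than a handful.

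A reader might infer that these subjects lose their safety follow-up, or that the efficacy results are at risk. Neither follows. Adverse event follow-up is timed from the last dose. Objective response is counted only up to progression or cessation of therapy, the PFS event is the progression itself, and OS does not depend on this visit.

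**What to change.** Add one sentence to footnote 13: *The PD visit may not serve as the treatment discontinuation visit for any subject dosed after it; the visit is then due 30 days (±7) after the actual last dose.*

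The cost is at most one already-defined visit per affected subject, which some may attend after starting a new therapy. No analysis, sample size or decision rule changes.

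Optional editorial tidying: a cross-reference to the pre-biopsy dosing rule in 5.5 and in the general stopping sentence of 5.3.

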## **8.2 BLOOD ANALYSES**

### **8.2.1 Blood for Germline DNA**

- This sample will be collected once prior to C1D1.
- Five (5) mL of blood will be collected

### **8.2.2 Blood for cfDNA Biomarker Research**

- This sample will be collected prior to C1D1 treatment and every 8 weeks until off treatment. If off treatment collection is within 2 weeks of prior collection, research samples do not need to be collected.
- 10 mL of blood will be collected

## **8.3 Confidentiality of Biospecimens**

Samples that are collected will be identified by a subject's study number assigned at the time of registration to the trial. Any material issued to collaborating researchers will be anonymized and only identified by the subject's study number.

## **9. CRITERIA FOR DISEASE EVALUATION**

For the purposes of this study, subjects should be re-evaluated for response every 8 weeks. Response and progression will be evaluated in this study using the new international criteria proposed by the Response Evaluation Criteria in Solid Tumors (RECIST) guideline (version 1.1) (23). Changes in the largest diameter (unidimensional measurement) of the tumor lesions and the shortest diameter in the case of malignant lymph nodes are used in the RECIST criteria.

### **9.1 Definitions**

Evaluable for Target Disease response. Only those subjects who have measurable disease present at baseline, have received at least one cycle of therapy, and have had their disease re-evaluated will be considered evaluable for target disease response. These subjects will have their response classified according to the definitions stated below. (Note: Subjects who exhibit objective disease progression prior to the end of cycle 1 will also be considered evaluable.)

Evaluable Non-Target Disease Response. Subjects who have lesions present at baseline that are evaluable but do not meet the definitions of measurable disease, have received at least one cycle of therapy, and have had their disease re-evaluated will be considered evaluable for non-target disease. The response assessment is based on the presence, absence, or unequivocal progression of the lesions.

## 9.2 Disease Parameters

Measurable disease. Measurable lesions are defined as those that can be accurately measured in at least one dimension (longest diameter to be recorded) as  $\geq 20$  mm by chest x-ray or  $\geq 10$  mm with CT scan, MRI, or calipers by clinical exam. All tumor measurements must be recorded in millimeters (or decimal fractions of centimeters).

**NOTE:** Tumor lesions that are situated in a previously irradiated area might or might not be considered measurable.

Malignant lymph nodes. To be considered pathologically enlarged and measurable, a lymph node must be  $\geq 15$  mm in short axis when assessed by CT scan (CT scan slice thickness recommended to be no greater than 5 mm). At baseline and in follow-up, only the short axis will be measured and followed.

Non-measurable disease. All other lesions (or sites of disease), including small lesions (longest diameter  $< 10$  mm or pathological lymph nodes with  $\geq 10$  to  $< 15$  mm short axis), are considered non-measurable disease. Bone lesions, leptomeningeal disease, ascites, pleural/pericardial effusions, lymphangitis cutis/pulmonitis, inflammatory breast disease, abdominal masses (not followed by CT or MRI), and cystic lesions are all considered non-measurable.

**NOTE:** Cystic lesions that meet the criteria for radiographically defined simple cysts should not be considered as malignant lesions (neither measurable nor non-measurable) since they are, by definition, simple cysts.

'Cystic lesions' thought to represent cystic metastases can be considered as measurable lesions, if they meet the definition of measurability described above. However, if non-cystic lesions are present in the same subject, these are preferred for selection as target lesions.

Target lesions. All measurable lesions up to a maximum of 2 lesions per organ and 5 lesions in total, representative of all involved organs, should be identified as target lesions and recorded and measured at baseline. Target lesions should be selected on the basis of their size (lesions with the longest diameter), be representative of all involved organs, but in addition should be those that lend themselves to reproducible repeated measurements. It may be the case that, on occasion, the largest lesion does not lend itself to reproducible measurement in which circumstance the next largest lesion which can be measured reproducibly should be selected. A sum of the diameters (longest for non-nodal lesions, short axis for nodal lesions) for all target lesions will be calculated and reported as the baseline sum diameters. If lymph nodes are to be included in the sum, then only the short axis is added into the sum. The baseline sum diameters will be used as reference to further characterize any objective tumor regression in the measurable dimension of the disease.

Non-target lesions. All other lesions (or sites of disease) including any measurable lesions over and above the 5 target lesions should be identified as non-target lesions and should also be recorded at baseline. Measurements of these lesions are not required, but the presence, absence, or in rare cases unequivocal progression of each should be noted throughout follow up.

